In animals, WS extracts have also been shown to be safe in toxicity studies. Acute and sub-acute toxicity of a hydroalcoholic root extract of WS was investigated in female Wistar rats.⁴⁴ No behavioral signs of toxicity or gross pathological changes were observed with acute doses up to 2000 mg/kg. Similarly, no signs of subacute toxicity were observed in rats given 500, 1000 or 2000 mg/kg of the extract daily for 28 days. In a separate study, a hydroalcoholic root extract of WS was used to assess prenatal developmental toxicity in rats at doses of 500, 1000 and 2000 mg/kg daily for 28 days.⁴⁵ No signs of toxicity, gross pathology changes, or mortality were observed in the pregnant rats or fetuses. Further studies are required to examine the safety of WS extracts prepared using other extraction methods and plant parts.

In humans, the widespread use of WS as a traditional medicine and dietary supplement, as well as current scientific literature, support its general safety. In a review of clinical trials that used root preparations of WS for a wide variety of conditions, the authors noted that reasonable safety outcomes were seen with no serious adverse events or changes in vital signs or hematological and biochemical parameters.⁴⁶ Mild to moderate transient adverse events including somnolence, giddiness, vertigo, drowsiness, and gastrointestinal effects (e.g., nausea, epigastric pain, loose stools, constipation, decreased appetite) were reported in some studies, while other studies involving adults and children did not report any adverse events.⁴⁶ Similarly, an earlier review reported that WS has been used in all age groups and in both sexes, even during pregnancy, without any reported side effects.¹⁰ One study formally measured the tolerability of a WS root extract using the Patient's Global Assessment of Tolerability to Therapy and found it to have a high tolerability score.⁴⁷ Rare, serious adverse events have been reported, however. Isolated cases of mild to severe liver toxicity have occurred, with three deaths in patients who had underlying liver disease.⁴⁸⁻⁵⁰ A case report has also been published detailing a kidney transplant rejection due to WS.⁵¹ Liver and renal abnormalities will be assessed at the beginning and end of each four-week study period.

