Study Title: Safety, tolerability, and pharmacokinetics of an oral *Withania somnifera* product in older adults

Principal Investigator: [name], ND, MS

IRB#: STUDY00026055

Version Date: 10.10.2024

F.2. Study Population

F.2.1. Number of participants

Twelve non-demented older volunteers (6 female, 6 male) 65 years of age or older will be screened and enrolled in the study. We estimate that we will need to screen approximately twenty potential participants to meet the twelve volunteers needed to complete the study. We expect two dropouts, for a total of 10 participants completing the study.

F.2.2. Inclusion and exclusion criteria

Inclusion criteria:

1. Age 65 and older, male and female
2. Body Mass Index (BMI) greater than 17 and less than 35 at screening
3. Sufficient vision and hearing to complete all tests
4. Willingness to discontinue all botanical supplementation for one week prior to and throughout study
5. No known sensitivity to *Withania somnifera* or any of its derivatives
6. Normal or clinically not significant 12-lead electrocardiogram (ECG) recording
7. Hepatic (ALT, AST, bilirubin), renal (creatinine, estimated GFR), and TSH parameters within normal range
8. Hemoglobin ≥ 13.0 g/dL or hematocrit $\geq 39\%$ (males) OR hemoglobin ≥ 12.5 g/dL or hematocrit $\geq 38\%$ (females), per FDA recommendations on blood donation
9. General health status that will not interfere with the ability to complete the study
10. Willingness to attend all study visits
11. Willingness to avoid caffeine and xanthine-containing foods or beverages (e.g., coffee, tea, chocolate, caffeine-containing sodas, colas, etc.), as well as grapefruit juice and poppy-containing foods for 48 hours prior to baseline visits
12. Willingness to adhere to special diet (no dairy, grapefruit products, poppy-containing foods, high-fat meals, caffeine, or xanthine-containing foods or beverages) during baseline visits and until after 24-hour visit
13. Mini-Mental State Exam (MMSE) score ≥ 27

Exclusion criteria:

1. Current smoking, alcohol, or substance abuse according to DSM-V criteria
2. Participants who are currently pregnant, actively trying to conceive a child, or planning to within three months of study completion
3. Severe aversion to venipuncture
4. Donation of blood within 90 days of screening
5. Participation in drug research study within 90 days of screening

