6. Serious health condition (i.e., illness, injury, impairment, or physical or mental condition which requires a) overnight hospitalization or b) continuing treatment that may cause episodic periods of incapacity of more than 3 consecutive days) within 30 days of screening
7. Allergy to nightshade plants (*Solanaceae* family)
8. Abnormal labs indicating symptomatic and untreated urinary tract infection
9. History of prostate cancer
10. History of kidney transplant
11. Cancer within the last five years, with the exception of non-metastatic skin cancers
12. Comorbid conditions requiring medication such as diabetes, kidney failure, liver failure, hepatitis, blood disorders, hypotension, thyroid disease, respiratory disorders, or cardiovascular disease
13. Presence of sleep apnea, moderate to severe restless leg syndrome, major circadian rhythm changes, or narcolepsy
14. Significant disease of the Central Nervous System (CNS) such as brain tumor, seizure disorder, subdural hematoma, cranial arteritis, or clinically significant stroke

15. Diagnosis of major depression, schizophrenia, bipolar disorder, or other major psychiatric disorder as defined by DSM-V criteria
16. Diseases associated with dementia such as Alzheimer's disease, vascular dementia, normal pressure hydrocephalus or Parkinson's disease

F.2.2.1. Allowable exceptions to inclusion/exclusion criteria:

1. Depression: Participants who report a diagnosis of depression, but (a) have a Geriatric Depression Scale score <5 at the screening visit (b) do not exhibit suicidal ideation, and (c) have been on a stable anti-depressant medication dose for at least two months prior to enrollment may be enrolled at the discretion of the clinical investigator.

F.2.2.2. Concomitant interventions

Allowed interventions: probiotic supplements, non-plant-based laxatives such as magnesium citrate or milk of magnesia, gastroesophageal reflux disorder medications such as antacids, dietary supplements that do not contain plant-based extracts, and non-narcotic analgesics

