After the consent form is signed the participant's health status will be evaluated using a biometric assessment (height, weight, and body mass index), vital signs (blood pressure, pulse rate, temperature, and respiration rate), a screening physical exam, a mood assessment (Geriatric Depression Scale-15), and cognitive assessment (Mini-Mental State Examination). A non-fasting plasma and urinary laboratory evaluation (complete blood count (CBC), comprehensive metabolic panel (CMP), thyroid-stimulating hormone (TSH), and urinalysis) will be performed and submitted to the OHSU clinical core laboratory to screen for abnormalities that could impact study results. Study staff will collect approximately three teaspoons (15 ml) of venous blood by peripheral venipuncture and the participant will collect 20 ml of urine via a clean-catch method for analysis. A screening electrocardiogram (ECG) will also be taken at the screening visit. The visit is expected to take 60 to 90 minutes.

The study clinician ([name]) will review screening and laboratory results with the candidate prior to participant enrollment. Participants will be contacted by phone and told whether they qualify for the study or not. Participants who meet all final eligibility criteria will be invited to participate in the intervention stage of the study. The OHSU research pharmacy will randomize

each participant into one of two dose sequence groups. Any participant with abnormal health screening or laboratory evaluation will be directed to their primary care physician for treatment and excluded from the study. In the event that a participant does not qualify for the study, their data will be destroyed at the end of the study.

I.4. PK Visits 1 and 2

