To reduce pregnancy risk, participants will be instructed at the Exit Phone Call to contact the study team if they believe they are pregnant or have fathered a child post-study. A records review will be conducted by a member of the study team one month after each participant has completed the study to check for reports and outcome of pregnancy.

N.1. Attribution to intervention

Items identified on the Adverse Event Monitoring Form will be compared to baseline levels to determine if the symptom was preexisting. If the symptom was pre-existing at the same or a previously greater severity, the symptom will not be considered attributable to the study intervention. If the symptom was pre-existing at lesser severity (or was not previously present), the symptom may be considered attributable to the study intervention. If the intervention is considered attributable, the co-investigators and the PI will determine if an alternative clinical explanation exists for the adverse event. If an alternative explanation does not exist, the adverse event *will* be considered attributable to the study intervention. If an alternative

Study Title: Safety, tolerability, and pharmacokinetics of an oral *Withania somnifera* product in older adults

Principal Investigator: [name], ND, MS

IRB#: STUDY00026055

Version Date: 10.10.2024

explanation does exist, the adverse event will *not* be considered attributable to the study intervention.

N.2. Plan for review and reporting

The study team will submit continuing review questionnaires to the OHSU IRB per institutional policy. The PI will review protocol deviations, reports, and AEs in real time to determine if they must be reported as Reportable New information (RNI). Events that are RNI will be reported to the OHSU IRB per RNI policy. All other events will be summarized and reported at continuing review.

O. RISKS AND BENEFITS

O.1. Risks to subjects

Potential harm to participants will be minimized by excluding participants with the conditions detailed in section F.2.2. The risks to the subjects participating in this proposed research project are mainly those associated with venous access, potential toxicity of the test material, and time commitment.

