Shoden® is commercially available and has been studied in randomized, double-blind, placebo-controlled clinical trials, where it has been well-tolerated with no significant adverse events reported.^{52,53,57} The doses of Shoden® being used in this study are 240 and 480 mg. In a previous clinical trial of 60 participants, 240 mg Shoden® once daily for 60 days was not associated with any significant adverse events or laboratory abnormalities.⁵³ The higher dose of 480 mg was studied in a recently completed study of Shoden®, where it was well-tolerated after a single administration in 16 participants.⁷⁹ We anticipate that 480 mg of Shoden® will also be safe and well-tolerated over four weeks, but will closely monitor participants for potential adverse events, as described in Section N. The widespread use of WS as a herbal dietary supplement¹ and reviews of clinical studies using WS^{46,86} supports its general safety. When side effects have been reported in clinical trials with other WS products, they have been mild to moderate transient effects including somnolence, giddiness, vertigo, drowsiness, and GI effects (e.g., nausea, epigastric pain, loose stools, constipation, decreased appetite).⁴⁶ There have also been rare reports of mild to severe liver toxicity for other WS products^{48,49} and a case of kidney transplant rejection in a patient using WS.⁵¹ There is also evidence that WS may modulate thyroid indices²⁰ and testosterone.⁵²⁻⁵⁵ Liver and renal abnormalities, thyroid function, and

Study Title: Safety, tolerability, and pharmacokinetics of an oral *Withania somnifera* product in older adults

Principal Investigator: [name], ND, MS

IRB#: STUDY00026055

Version Date: 10.10.2024

testosterone will be assessed at the beginning and end of each four-week study period. The risk of taking WS while pregnant or breast-feeding is unknown and therefore, it is recommended to avoid WS during pregnancy and breast-feeding.

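### Exclusion 12 reaches liver disease only when it needs medication, so known, unmedicated liver disease with normal screening results is barred by no criterion; O.1 also omits the deaths reported in C.2.3

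*Combined protocol and SAP*

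**What the plan says.** The safety background in C.2.3 states: "Isolated cases of mild to severe liver toxicity have occurred, with three deaths in patients who had underlying liver disease". Three references (48 to 50) support that sentence. O.1 assigns risk control to eligibility: "Potential harm to participants will be minimized by excluding participants with the conditions detailed in section F.2.2".

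Within F.2.2, liver disease appears by name in one place. Exclusion 12 begins "Comorbid conditions requiring medication such as diabetes, kidney failure, liver failure, hepatitis" and continues with further examples. Inclusion 7 adds a laboratory condition: "Hepatic (ALT, AST, bilirubin), renal (creatinine, estimated GFR), and TSH parameters within normal range". Section I.3 adds a general screening rule: "Any participant with abnormal health screening or laboratory evaluation will be directed to their primary care physician for treatment and excluded from the study".

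O.1 returns to hepatic risk with "There have also been rare reports of mild to severe liver toxicity for other WS products". It cites references 48 and 49 and does not mention deaths.

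**The concern.** C.2.3 identifies the risk factor in the fatal cases as existing liver disease. Exclusion 12 tests something else: whether a comorbid condition needs drug treatment. A chronic liver disease can be diagnosed and followed without medication, and exclusion 12 does not apply to such a person.

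Two things are at stake. The first is safety. The protocol leaves hepatic risk reduction to F.2.2, and each participant is scheduled for two single doses plus two courses of 28 daily doses, that is 2 + 2 × 28 = 58 dosing days. The experience cited for the higher dose is a single administration in 16 people, and E.2 gives the age range in the 480 mg study as 18 to 45.

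The second is interpretation. Aim 2 concerns tolerability in older adults, and A.1 describes the population as healthy. Under N.1, an adverse event is not attributed to the product if another clinical explanation exists. In a participant with known liver disease that alternative is always available, so a liver event would be hard to read in a study of 12.

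**Working it through.** No arithmetic settles this point, and the plan states no figure to reproduce. The check sets every rule that bears on liver disease side by side and asks what is left.

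**Rules that can keep a person with liver disease out**

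- *Exclusion 12 (F.2.2).* Applies if the condition needs medication. The named conditions are examples, so other drug-treated liver disease is covered as well. The medication qualifier is the only real limit.
- *Inclusion 7 (F.2.2).* Applies if ALT, AST or bilirubin is out of range. It makes no allowance for results judged clinically unimportant, unlike inclusion 6 on the ECG.
- *Screening rule (I.3).* Applies if the screening or laboratory evaluation is abnormal. That evaluation includes a blood count, a metabolic panel, urinalysis and a physical examination, and the study clinician reviews the results before enrolment.
- *Exclusion 1.* Current alcohol abuse only.
- *Exclusion 6.* Serious illness within 30 days of screening, defined by hospital stay or incapacity.
- *Inclusion 9.* "General health status that will not interfere with the ability to complete the study". This concerns completing the study, not hepatic risk.

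**What remains.** Write D for a diagnosed chronic liver disease, M for a need for medication, L for an out-of-range ALT, AST or bilirubin, and S for any other abnormal screening finding. The first three rules exclude D when M or L or S holds. They admit D when M, L and S are all absent. The last three rules remove some individuals from that group for other reasons, but none of them is triggered by the diagnosis itself.

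**How the plan treats its other Withania signals**

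- *Kidney.* C.2.3 cites one case report of transplant rejection. Exclusion 10 bars a past transplant outright.
- *Prostate.* C.2.3 cites testosterone rises of 11% and 14.7% in two trials of this product. Exclusion 9 bars past prostate cancer outright.
- *Liver.* C.2.3 cites three deaths. Exclusion 12 applies only with medication.

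The plan gives no reason why the signal that includes deaths should carry the additional qualifier.

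**C.2.3 against O.1.** Both describe mild to severe liver toxicity. C.2.3 adds the three deaths and cites references 48, 49 and 50. O.1 omits the deaths, omits reference 50 and confines the reports to other products. This difference can be confirmed by reading the two sections and does not depend on the eligibility argument.

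**The case against.** The strongest reply is that exclusion 12 is not the only barrier. Inclusion 7 is strict, the I.3 rule is broad, and a clinician sees the whole screening record before anyone is enrolled. A.1 also describes the participants as healthy. Together these should stop most people with active or advanced liver disease. That stands, and it narrows the point considerably. It does not close the gap: normal results on one screening sample do not show that a diagnosed disease is absent, the evaluation set out in I.3 does not list a prior diagnosis as a ground for exclusion, and the description in A.1 is not a criterion.

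A reader might infer that the very group in which deaths occurred can be enrolled. The documents do not support that. C.2.3 gives no disease type, severity, liver tests or medication status for the fatal cases. Those patients might have failed inclusion 7 or exclusion 12, or might not; the protocol does not say.

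A reader might also want the chance that at least one of the 12 participants belongs to the residual group. That needs a prevalence among people who have already passed the liver tests and the screening evaluation, and none is given. Any percentage would rest on an invented input.

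On O.1, it is fair to answer that the deaths appear in C.2.3 of the same protocol, so they have not been withheld from the ethics board. That makes the omission an internal inconsistency. Nothing follows about the consent form, which is not part of the text available here.

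**Conclusion.** The point holds in a limited form. Followed as written, the plan would admit a person with a known chronic liver disease that needs no medication, provided ALT, AST, bilirubin and the rest of the screening evaluation were normal. This sits poorly with C.2.3, which names existing liver disease as the setting of the deaths, with O.1, which relies on F.2.2 for protection, and with exclusions 9 and 10, which act on history alone. Separately, O.1 gives a less complete account of hepatic risk than C.2.3.

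The size of the residual group is unknown and may be small once inclusion 7 and the I.3 rule have acted. The conclusion rests on two readings: that the medication qualifier in exclusion 12 governs the whole list of examples, and that a reported diagnosis with normal findings does not itself count as an abnormal health screening under I.3. If the sponsor intends otherwise on either, the text should say so. The correction is worth making because it is cheap and concerns the gravest outcome the protocol reports.

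**What to change.** Reconcile exclusion 12 with C.2.3, inclusion 7, I.3 and the opening of O.1, so that known liver disease is addressed by diagnosis or history and not only through the need for medication. Which liver diagnoses to cover is for the sponsor and the study clinician to decide and justify. The information is already within reach: K.1 lists a medical history form among the case report forms, and section G provides for chart review of candidates found through the electronic records.

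In O.1, carry over the statement on the three deaths from C.2.3, with reference 50, and confirm that the consent form agrees.

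The cost is an amendment to one eligibility clause and one added sentence. The downside is an occasional extra screen failure among the roughly 20 people expected to be screened for 12 places. No visit, assay or analysis changes.
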